	
9. Negative COVID-19 test for subjects with COVID-19 symptoms or who have had direct exposure to someone with a positive COVID-19 test, as determined by the Investigator.
 
Exclusion criteria:
 
1. Any history of schizophrenia or schizoaffective disorder.2. Any other current Axis I disorder, including, but not limited to, major depressive disorder, bipolar disorder, post-traumatic stress disorder, obsessive-compulsive disorder, premenstrual dysphoric disorder, and generalized anxiety disorder, which is in poor control and the primary focus of treatment.3. A diagnosis of social anxiety disorder.4. A score >60 on the LSAS at Screening (Visit 1).5. Subjects who meet criteria for moderate or severe alcohol or substance use disorder within 1 year prior to study entry.6. In the opinion of the Investigator, the subject has a significant risk for suicidal behavior during their participation in the study, or
a. At Screening (Visit 1): the subject scores "yes" on items 4 or 5 in the Suicidal Ideation section of the Columbia-Suicide Rating Scale (C-SSRS) with reference to a 6-month period prior to screening; orb. At Screening (Visit 1): the subject has had one or more suicidal attempts with reference to a 2 -year period prior to screening; orc. At Baseline (Visit 2): the subject scores "yes" on items 4 or 5 in the Suicidal Ideation section of the C-SSRS with reference to screening; ord. The subject is considered to be an imminent danger to themselves or others.7. Clinically significant nasal pathology or history of significant nasal trauma, nasal surgery, total anosmia, or nasal septum perforation that may have damaged the nasal chemosensory epithelium.8. An acute or chronic condition, including an infectious illness, uncontrolled seasonal allergies at the time of the study, or significant nasal congestion that potentially could affect drug delivery to the nasal chemosensory epithelium. The Investigator may allow concomitant use of over-the-counter nasal decongestants as needed, since there is no apparent drug interaction between these and PH94B.9. Concomitant use of any anxiolytics, such as benzodiazepines, buspirone, or cannabinoids during the study and within 30 days of Baseline (Visit 2).10. Concomitant use of any over-the-counter, prescription product, or herbal preparation for treatment of the symptoms of anxiety during the study and within 30 days before study entry. Selective serotonin reuptake inhibitors, serotonin-norepinephrine reuptake inhibitors, or other approved antidepressants are permitted if the dose has been stable for 30 days prior to Baseline (Visit 2).11. Women who have a positive urine pregnancy test prior to IP administration or are currently breast feeding.12. Subjects with clinically significant abnormalities in hematology, blood chemistry, urinalysis, ECG, or physical examination identified at the Screening visit that in the clinical judgment of the Investigator, could place the subject at undue risk, interfere with study participation, or confound the results of the study.13. Subjects with a positive urine drug screen at either Screening (Visit 1) or Baseline (Visit 2).14. Any current clinically significant and/or uncontrolled medical condition, based on medical history or as evidenced in screening assessments, such as COVID-19, HIV, cancer, stroke, congestive heart failure, uncontrolled diabetes mellitus, or any other medical condition or disease that, in the clinical judgment

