10. Concomitant use of any over-the-counter, prescription product, or herbal preparation for treatment of the symptoms of anxiety during the study and within 30 days before study entry. Selective serotonin reuptake inhibitors, serotonin-norepinephrine reuptake inhibitors, or other approved antidepressants are permitted if the dose has been stable for 30 days prior to Baseline (Visit 2).
11. Women who have a positive urine pregnancy test prior to IP administration or are currently breast feeding.
12. Subjects with clinically significant abnormalities in hematology, blood chemistry, urinalysis, electrocardiogram, or physical examination identified at Screening(Visit 1) that in the clinical judgment of the Investigator, could place the subject at undue risk, interfere with study participation, or confound the results of the study.
13. Subjects with a positive urine drug screen at either Screening(Visit 1) or Baseline(Visit 2).

14. Any current clinically significant and/or uncontrolled medical condition, based on medical history or as evidenced in screening assessments, such as COVID 19, HIV, cancer, stroke, congestive heart failure, uncontrolled diabetes mellitus, or any other medical condition or disease that, in the clinical judgment of the Investigator, could place the subject at undue risk, interfere with study participation, or confound the results of the study.
15. Use of a concomitant medication that, in the clinical judgment of the Investigator, could place the subject at undue risk, interfere with study participation, or confound the results of the study.
16. History of cancer or malignant tumor not in remission for at least 2 years. Basal cell skin cancers are not exclusionary.

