9.7.2 Prohibited Therapies

With the exception of concomitant medications for the treatment of insomnia described in Section 9.7.1, no other psychotropic medication besides IP is permitted to be used by any subject between Screening (Visit 1) and Follow-up (Visit 7). Prohibited psychotropic medications include centrally acting medications used to treat pain and muscle spasms, such as gabapentin and cyclobenzaprine.

Prior use of PH94B is not permitted.

Where washout of prohibited medications is required before randomization, tapering rates are at the discretion of the Investigator and are to be determined on an individual basis, with consideration to subject state, dose, and known pharmacokinetics of the medication being discontinued. The subject must be consented before any tapering is started. If the washout of the anti-anxiety medications makes the subject clinically unstable, the Investigator has the discretion to not to proceed with the subject in the study.

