10.2. Study Periods and Visits

10.2.1 Screening and Washout

10.2.1.1 Screening (Visit 1)

Screening begins after the written informed consent has been obtained from the subject. The purpose of the screening phase is to:

- Ensure that appropriate subjects are entered into the trial
- Determine that the subject meets all eligibility criteria
- Collect demographic and medical data permitting characterization of the subject
- Ensure that prohibited medications are discontinued

To meet these objectives, the duration of screening can be up to 35 days if taper of prohibited medication is required. Subjects continuing to meet all eligibility requirements at Baseline (Visit 2) will be randomized and dispensed double-blinded IP.

All subjects agreeing to participate must give written informed consent using the IRB-approved ICF before any study-related procedures are performed (including tapering of prohibited medications). The ICF will be signed and dated by the subject and Investigator or other appropriate site staff, and a copy of the signed ICF will be given to the subject. The informed consent process will be documented in the source records for each subject.

After the ICF process is complete, a subject number will be allocated by the site, by assigning the next sequential subject number available.

The following procedures will be performed at Screening (Visit 1), which is to occur at least 7 days, but no more than 35 days prior to Baseline (Visit 2):

- Obtain informed consent
- Collect demographic information
- Assign subject number, as described above

- Obtain medical history (including nicotine, alcohol and cannabis use, and menstrual information on women of childbearing potential) and psychiatric history
- Record prior and concomitant treatment and medication use (medication name, dose, and frequency)
- Administer MINI 7.0.2
- Perform physical examination, including height (inches), body weight (pounds), body temperature (°F), and clinical examination of both nasal passages
- Measure vital signs after the subject has rested for 5 minutes: seated systolic and diastolic blood pressure, heart rate, respiratory rate, and body temperature
- Obtain 12-lead ECG
- Obtain blood and urine samples for clinical laboratory examination, including hematology, chemistry, prolactin, thyroid functioning, and urinalysis (refer to Section 10.3.2.1.1 for complete list)

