10.2.1.2 Washout Period

Subjects requiring washout of prohibited concomitant medications such as benzodiazepines must have stopped taking these medications 30 days prior to Baseline (Visit 2). Selective serotonin reuptake inhibitors, serotonin-norepinephrine reuptake inhibitors, and other antidepressants are allowed so long as the dose has been stable for 30 days prior to Baseline (Visit 2).

Refer to Section 9.7.2 for more information concerning washout procedures.

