10.3.2.1 Clinical Laboratory Safety Assessments

10.3.2.1.1 Clinical Laboratory Tests to be Performed

Samples for the following laboratory tests will be collected at the time points specified in the schedule of events (Table 2-1).

All laboratory tests will be performed on site during the study, and include the following:

Chemistry Panel:	alanine aminotransferase, aspartate aminotransferase, albumin, calcium, chloride, alkaline phosphatase, bicarbonate, cholesterol, creatine kinase, creatinine, direct bilirubin, lactate dehydrogenase, magnesium, globulin, glucose, gamma-glutamyl transferase, indirect bilirubin, phosphorous, potassium, sodium, total bilirubin, total protein, triglycerides, urea nitrogen, uric acid
Hematology/ Hemogram Panel:	hematocrit, hemoglobin, mean corpuscular hemoglobin, mean corpuscular concentration, mean corpuscular volume, platelets, red blood cell count, white blood cell count, red blood cell morphology
Hematology Differential Panel:	basophils, eosinophils, lymphocytes, monocytes, neutrophils
Urinalysis macroscopic panel:	bilirubin, blood, clarity, color, glucose, ketones, leucocyte esterase, nitrite, pH, protein, specific gravity, urobilinogen
Urine Pregnancy Test:	for all female subjects of childbearing potential
Urine Drug Screen:	tricyclic antidepressants, opiates, cocaine, benzodiazepines, amphetamines, barbiturates, cannabinoids, methadone, methamphetamine, phencyclidine, propoxyphene, buprenorphine, ecstasy, oxycodone

- Other:
 - prolactin
 - thyroid stimulating hormone
 - free thyroxine (T4) (if thyroid stimulating hormone is above the upper or below the lower normal limits, then free thyroxine will automatically be performed)

The local laboratory should be used for any unscheduled and follow-up labs, if needed. This includes any confirmatory pregnancy or drug screens for positive urine tests. Additional urine and blood samples may be collected for further evaluation of safety as warranted by the Investigator's judgment.

Results and reports from the local laboratory should be filed with the source documents for each subject. The local laboratory will provide results to the study site staff as soon as they are available and will be provided to sponsor or designated data manager within agreed timelines.

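### Protocol 9.7.2 bans the stable-dose antidepressants that exclusion 10 and 10.2.1.2 permit, and the SAP does not say which list defines a prohibited medication

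*Protocol*

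**What the plan says.** **The ban.** Protocol 9.7.2 exempts the 9.7.1 insomnia medicines and otherwise states that "no other psychotropic medication besides IP is permitted to be used by any subject between Screening (Visit 1) and Follow-up (Visit 7". It does not mention antidepressants.

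**The permission.** Exclusion 10, in the synopsis and again in 8.2.2, covers SSRIs and SNRIs and adds: "or other approved antidepressants are permitted if the dose has been stable for 30 days prior to Baseline (Visit 2". Section 10.2.1.2 agrees: "other antidepressants are allowed so long as the dose has been stable for 30 days prior to Baseline (Visit 2".

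**The cross-references.** Sections 9.7 and 9.7.1 contain almost the same sentence letting medicines started before Screening continue. In 9.7 the exceptions are those in 8.2.2; in 9.7.1 they are those in 9.7.2. Section 8.3, on withdrawal, cites 9.7.2.

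**Screening.** One stated purpose of Visit 1 is to "Ensure that prohibited medications are discontinued". Under 10.2.1.2, subjects needing washout of prohibited drugs "must have stopped taking these medications 30 days prior to Baseline (Visit 2", and 10.2.1.1 says "the duration of screening can be up to 35 days if taper of prohibited medication is required".

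**The SAP.** Section 6.1.4 and Table 3 treat use of a prohibited medication before Week 4 as an intercurrent event, after which the Visit 6 HAM-A becomes missing. Section 7.2 lists such use as an example of an important deviation. Neither section gives a drug list or a protocol section number, and Protocol Table 13-1 gives none either.

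**The concern.** For a subject on a stable SSRI, the protocol gives two opposite instructions, and each comes from a section that sites or analysts would reasonably treat as authoritative.

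Two things are at stake. The first is conduct and subject welfare: an eligible person could be taken off an effective antidepressant quickly, turned away or withdrawn. The enrolled population would then be narrower than the one in the estimand, which Protocol 13.1.1.1 and SAP Table 4 define by the inclusion and exclusion criteria. The second is the primary analysis: an observed Visit 6 HAM-A could be discarded because of a treatment that the entry criteria allow.

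**Working it through.** The plan states no figure on this point, so the check compares the texts and then works out the consequence of each reading.

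**1. What each section implies for a subject on a stable SSRI**

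| Section | Stable SSRI |
|---|---|
| Synopsis and 8.2.2, exclusion 10 | permitted |
| 10.2.1.2 | permitted |
| 9.7 (exceptions from 8.2.2) | may continue |
| 9.7.2 | banned, Visit 1 to Visit 7 |
| 9.7.1 (exceptions from 9.7.2) | may not continue |
| 8.3 (cites 9.7.2) | investigator may withdraw |
| SAP 6.1.4, Table 3, 7.2 | depends on a list not named |

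There are two controlling lists, 8.2.2 and 9.7.2, and they disagree.

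**2. Can 9.7.2 be read so that the conflict disappears?** Taking psychotropic to leave out antidepressants is hard to sustain. The ban extends to gabapentin and cyclobenzaprine, and low-dose doxepin escapes it only through the insomnia exception. Taking it to cover only newly started drugs is also hard, because it applies to every subject from Screening and the same section describes washout before randomization.

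**3. Consequences under three readings**

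*Reading A: 8.2.2 controls.* Scores lost to this cause: 0.

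*Reading B: sites apply 9.7.2 literally.* Inputs: a screening maximum of 35 days (10.2.1.1) and 30 drug-free days before Baseline (10.2.1.2). Tapering may not start before consent (9.7.2).
- Time to taper = 35 − 30 = 5 days at most.
- No Visit 6 score is replaced for continued use, because continuing users are not enrolled or do not stay.

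*Reading C: sites enrol under exclusion 10, and 9.7.2 then defines the SAP event.* Inputs: 40 randomized 1:1 (synopsis) and the 0.05 switch in SAP 6.1.4. Assume all 40 are in the ITT population and no other score is missing. Fraction missing = users / 40.
- 1 user: 1/40 = 0.025, so the treatment-group mean change is inserted.
- 2 users: 2/40 = 0.050, not above 0.05, so the group mean is again inserted.
- 3 users: 3/40 = 0.075, above 0.05, so multiple imputation is used.

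The documents give no rate of antidepressant use. For assumed rates, the binomial probability of at least 3 users among 40 is:

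| Assumed use | P(at least 3 of 40) |
|---|---|
| 5% | 0.32 |
| 10% | 0.78 |
| 15% | 0.95 |
| 20% | 0.99 |

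These probabilities matter only under reading C and say nothing about how likely that reading is.

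**4. A related gap.** Exclusion 13 begins "Subjects with a positive urine drug screen at either", and the urine panel in 10.3.2.1.1 starts with "tricyclic antidepressants, opiates, cocaine, benzodiazepines, amphetamines". A stable tricyclic falls within the permission in exclusion 10 but may fail exclusion 13. This does not depend on 9.7.2 and adds no weight to the main point.

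**The case against.** The strongest reply is that this is a drafting omission that no careful reader would act on. Three specific permissions stand against one general sentence that never names antidepressants. Section 9.7.2 cannot be meant absolutely from Visit 1, since it allows tapering after consent. Section 10.2.1.2 permits stable antidepressants and then refers to 9.7.2 for washout, as though the two agreed. Section 9.7 names 8.2.2 and tells sites to ask the Medical Monitor when unsure, and the SAP has a blinded review before lock.

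Most of this stands as evidence of intent and as mitigation. It does not settle the matter. A site that reads only one of the sections would not be unsure and so would not ask, and neither the Medical Monitor provision nor the blinded review says which list governs.

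A reader might also infer more than the documents support:
- **That the three sections name three different lists.** They name two; 9.7.1 and 8.3 agree with each other.
- **That the SAP event has no source at all.** The SAP names the protocol as its reference, so the term inherits two conflicting answers.
- **That the imputation model is at fault for lacking an antidepressant variable.** Under reading C every user's Visit 6 score is missing, so no user outcome would be observed from which to estimate such an effect. With one or two users and nothing else missing, no model is fitted.
- **That a loss of precision can be attached to this defect.** Any such figure would depend on an assumed number of users and, in part, on the SAP's imputation model.
- **That the important-deviation label changes the efficacy result.** SAP 7.2 excludes such subjects from a per-protocol population that SAP Section 5 does not define, and efficacy is analysed in the ITT population.

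**Conclusion.** The contradiction is real, and the text of 9.7.2 is wrong as written. It should be fixed, but it is not a fatal flaw. On the likely intended reading no score is lost. If sites follow 9.7.2 literally, the harm is to eligible subjects and to the match between the enrolled and target populations, with at most 5 days to taper if the 30-day rule is applied. Only under the mixed reading is an observed primary outcome discarded. There, 3 users among 40 ITT subjects change the primary missing-data method, assuming no other missing scores.

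It would be tempting to conclude that the primary analysis will lose data or be biased. The documents do not support that: they give no number of users, and the loss requires sites and analysts to apply different lists to the same subjects.

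**What to change.** **Protocol, by amendment.**
- Add to 9.7.2 an exemption for antidepressants continued at a dose stable for 30 days before Baseline.
- Make 9.7, 9.7.1 and 8.3 refer to that one list.
- As a secondary tidy-up, state whether tricyclics fall under the exemption. If they do, say that a positive tricyclic screen explained by a documented stable prescription does not exclude.

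**SAP, before unblinding.** Define the event in 6.1.4 and Table 3 as use, after randomization and before the Visit 6 (Week 4) assessment, of a drug prohibited by the corrected 9.7.2.
- Include a prohibited drug continued through Baseline, and an antidepressant newly started or changed in dose.
- Exclude antidepressants continued at the stable dose allowed at entry.
- Keep the Week 4 limit. The 9.7.2 ban runs to Visit 7, so an event defined as any use after Baseline could delete a valid Visit 6 score because of a drug first taken in the follow-up week.

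**Cost.** Protocol 14.8 requires a formal amendment with sponsor approval, investigator signature and IRB approval. The SAP needs a short definition. No new data, visits or subjects are needed.

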9.7.3 Restrictions

Subjects who meet criteria for moderate or severe alcohol or substance use disorder (including cannabinoids) within the 1 year prior to study entry will be excluded from the study.

9.8. Treatment After End of Study

After the end of the study, each subject will be treated according to standard clinical practice.

9.9. Dispensing and Storage

The test product supplied by [REDACTED] is to be used exclusively in the clinical study according to the instructions of this protocol. The Investigator is responsible for dispensing the IP according to the dosage scheme and for ensuring proper storage of the IP.

The Investigator must confirm the receipt of the IP with his or her signature. A copy of this receipt must be kept by the Investigator and another copy will be stored at VistaGen Therapeutics, Inc. and at Premier Research.

All IP supplied to each site by the sponsor will be maintained in a safe and secure (locked) area, stored [REDACTED] until dispensed, and [REDACTED]

[REDACTED] Access should be restricted to the designated responsible member/s of the Investigator's staff and to the clinical monitor. The Investigator agrees that neither he/she nor any of the study staff will supply IP to any person other than subjects enrolled in the study.

The key to the storage area is to be kept by the Investigator or designee responsible for the IP. The store will be accessible only to those persons authorized by the Investigator to dispense the IP.

9.10. Drug Accountability

Upon receipt of each IP shipment, an inventory must be performed, and a drug receipt log filled out and signed by the person accepting the shipment. It is important that the designated study staff counts and verifies that the shipment contains all the items noted in the shipment inventory. Any damaged or unusable IP in a given shipment (active drug or comparator) must be documented in the study files and reported immediately to the monitor.

9.11. Labeling and Packaging

Labeling and packaging of the IPs will be performed by [REDACTED]

[REDACTED]

9.11.1 Labeling

The vials will have a label affixed that meets the applicable regulatory requirements and may include the following: subject identifier, IP name, dosage strength, lot number, protocol number, specified volume of contents, caution statement ("New Drug – Limited by United States Law to Investigational Use" and "Keep out of reach of children"), storage, and sponsor identification.

Investigators must save all empty packaging or packaging containing used and unused vials for final disposition by the sponsor or contract pharmacy.

9.11.2 Packaging

IP will be supplied in amber glass vials. The spray delivery device consists of an actuator and a 10-mL amber glass vial.

10. STUDY PROCEDURES

Subjects must provide written informed consent before any study-related procedures are initiated, including the cessation and taper of prohibited concomitant therapy.

For the timing of assessments and procedures throughout the study, refer to the schedule of events ([Table 2-1](#)). Throughout the study, every reasonable effort should be made by study personnel to follow the timing of assessments and procedures in the schedule of events for each subject. If a subject misses a study visit for any reason, the visit should be rescheduled as soon as possible. The same trained rater should complete the appropriate assessment with the subject for all visits.

10.1. Study Duration

The study comprises a screening period of up to 35 days, a double-blind phase of 4 weeks, followed by a follow-up visit approximately 1 week later.

